## **STUDY METHODS**

### **I. Recruitment**

- a) Patients of the investigators will be recruited for this study during their preoperative outpatient appointments approximately one week before surgery. The study material packet containing the HIPAA and the informed consent form will be emailed to the patient for review. Thus the patient will have adequate time to ask questions and consider the study prior to scheduled surgery.
- b) The patients will be contacted by one of the study investigators the morning of surgery at which time a signed consent will be obtained.
- c) Only patients who have provided their written consent and indicated that they have been introduced to the study prior to meeting with the anesthesiologists on the day of surgery will be able to participate.
- d) Screening procedures will make sure patients meet all inclusion criteria.

### **II. In the preoperative holding area:**

- a) An anesthesia investigator assigned to the specific case will assess patients and perform a pre-operative anesthesia assessment as per standard protocol at CSMC. None of this data will be recorded until written informed consent is obtained.
- b) Patients will provide a detailed medical history including demographic information (e.g., age, weight, height, ethnic origin, smoking history, history of motion sickness, history of postoperative nausea and vomiting, as well as chronic analgesic usage). None of this data will be recorded until written informed consent is obtained.
- c) Written informed consent will be obtained by one of the investigators.
- d) Patients will be randomized in a blinded fashion by study staff to one of the groups via online randomization site, sealedenvelope.com, in a 2:2:1 fashion.

Group 1	n=100	Ultrasound guided TAP Block
Group 2	n=100	Laparoscopic guided TAP Block
Group 3	n=40	No TAP

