## Data Analysis

### Primary outcome measure:

With a sample size of 100 in each TAP block arm, a two group 0.025 one-sided t-test will have 80% power to reject the null hypothesis that the two groups are not equivalent in morphine (mg) use in the first 24 hours after surgery and rule in favor of the alternative hypothesis that the mean morphine use in the first 24 hours after surgery is equivalent for the two groups or the difference in means ( $\bar{x}_T - \bar{x}_S$ ) is 10 or farther from zero in the same direction, assuming that the expected difference in means is 0 and the common standard deviation is 25.

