### Secondary outcome measure:

To show superiority of TAP to No TAP a two group t-test with a 0.05 two-sided significance level will have 88% power to detect the difference between a Control Group 1 (No TAP block) mean,  $\bar{x}_1$ , of 60 mg morphine use in the first 24 hours after surgery and a Group 2 (TAP block) mean,  $\bar{x}_2$ , of 45 mg morphine, a difference in means of 15, assuming that the common standard deviation is 25 mg, when the sample sizes in the two groups are 40 and 100, respectively.

Thus total number of patients to show non-inferiority between ultrasound-guided and laparoscopic-guided TAP block, and superiority of either technique to no TAP is 240 patients. Allowing for a 5% drop out rate (n=12 patients), the total number of patients we anticipate to recruit is 252.

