## SUBJECT RECRUITMENT

1. The subjects will be approached regarding the study during their preoperative consultation visit. If patient indicates a willingness to participate and meets the inclusion criteria and does not meet any exclusion criteria, they will be handed, emailed, or mailed a copy of the consent form to read, and the study will be scheduled at least 24 hours after they have received the consent form to review. The consent form will detail the purposes,

procedures, possible risks and benefits of the study. The informed consent form will have a contact number for the investigators to allow subjects to ask questions prior to the day of surgery.

2. Subjects must give informed consent to participate in the study.
3. When the patient arrives for the surgery, a study investigator will meet with the patient and discuss the procedure in detail in the preoperative holding area, and provide another copy of the informed consent for the patient to review and sign.
4. After the patient has signed informed consent, they will be randomized to one of three study arms by the study staff.

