## **INCLUSION CRITERIA**

A total of 252 patients undergoing laparoscopic colorectal procedures

Willingness and ability to sign an informed consent document

No allergies to anesthetic or analgesic medications

ASA physical status Class I – III adults of either sex

Aged 18-90 years

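### The stated 2:2:1 randomisation ratio does not match the planned arms of 100, 100 and 40, which are 5:5:2; the effect on power is minor

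*Combined protocol and SAP*

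**What the plan says.** Study Methods II (In the preoperative holding area), item d, has study staff allocate patients "via online randomization site, sealedenvelope.com, in a 2:2:1 fashion". The table directly below gives Group 1 (ultrasound-guided TAP) n=100, Group 2 (laparoscopic-guided TAP) n=100 and Group 3 (No TAP) n=40.

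The Data Analysis section uses the table's arm sizes:

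- The primary outcome paragraph begins "With a sample size of 100 in each TAP block arm" and claims 80% power.
- The secondary outcome paragraph claims 88% power for TAP against No TAP "when the sample sizes in the two groups are 40 and 100, respectively".
- It then gives the total for non-inferiority plus "superiority of either technique to no TAP is 240 patients", and after a 5% dropout allowance of 12 patients, "the total number of patients we anticipate to recruit is 252".

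Inclusion Criteria repeats the 252. Subject Recruitment, item 4, says only that "they will be randomized to one of three study arms by the study staff" and gives no ratio.

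**The concern.** The ratio and the arm sizes stand next to each other and disagree. The arm sizes cannot be dismissed as a slip in the table, because both power statements use them and 100 + 100 + 40 = 240 is the stated total. The ratio is the figure that departs from the rest.

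An allocation ratio is an operational setting that someone has to enter in the online randomisation system. If 2:2:1 is entered literally, some patients meant for the TAP arms go to No TAP. The primary comparison is between the two TAP arms and was sized with almost no slack, so it loses a little power, while the comparison with No TAP gains some. A later reader comparing the achieved arm sizes with the protocol also could not tell whether randomisation had run as planned.

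**Working it through.** **Inputs, all from the document.** Ratio 2:2:1 and arms 100/100/40 (Study Methods II, item d). Primary comparison: margin 10 mg, expected difference 0, SD 25 mg, one-sided α 0.025, 100 per arm (Data Analysis, primary outcome, and the table that follows it). Superiority comparison: 60 versus 45 mg, so a difference of 15 mg, SD 25 mg, two-sided α 0.05, 40 versus 100 (secondary outcome). Total 240, dropout 5%, recruitment 252.

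**Step 1. Can ratio, arms and total agree?**

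- 100:100:40, divided by 20, is 5:5:2.
- 2:2:1 with 40 in No TAP: 80 + 80 + 40 = 200.
- 2:2:1 with 100 per TAP arm: 100 + 100 + 50 = 250.
- 2:2:1 with a total of 240: 240 × (2/5, 2/5, 1/5) = 96, 96, 48.
- 2:2:1 with 252 randomised: 100.8, 100.8, 50.4; after 5% loss (× 0.95): 95.76, 95.76, 47.88.
- 5:5:2 with 252 randomised: 252 × (5/12, 5/12, 2/12) = 105, 105, 42; after 5% loss: 99.75, 99.75, 39.9.

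Only 5:5:2 recovers the listed arms from the stated totals. The dropout allowance does not explain the difference.

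**Step 2. Reproduce the stated power.** SE = σ√(1/n₁ + 1/n₂), noncentrality λ = Δ/SE, df = n₁ + n₂ − 2, and power = P(T > t_crit), where T is noncentral t with noncentrality λ. Here t_crit is the upper 2.5% point for both tests.

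- Non-inferiority at 100 per arm: SE = 25√(2/100) = 3.536; λ = 10/3.536 = 2.828; df = 198; t_crit = 1.972; power 80.4% (80% stated).
- Superiority at 40 versus 100: SE = 25√(1/40 + 1/100) = 4.677; λ = 15/4.677 = 3.207; df = 138; t_crit = 1.977; power 89.0% (88% stated).

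Both stated figures therefore rest on 100/100/40.

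**Step 3. Same calculation at 2:2:1 with 240 evaluable (96/96/48).**

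- Non-inferiority: SE = 25√(2/96) = 3.608; λ = 2.771; df = 190; power 78.7%.
- Superiority, 48 versus 96: SE = 25√(1/48 + 1/96) = 4.419; λ = 3.394; df = 142; power 92.1%.

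Eight evaluable patients (4 + 4) move from the TAP arms to No TAP.

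**Step 4. Same 252 randomised, the two ratios compared.** Loss is assumed equal across arms.

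| | Non-inferiority, 2:2:1 | Non-inferiority, 5:5:2 | Superiority, 2:2:1 | Superiority, 5:5:2 |
|---|---|---|---|---|
| No loss | 80.7% | 82.2% | 93.3% | 90.4% |
| 5% loss | 78.6% | 80.3% | 92.0% | 88.9% |

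**Step 5. Where does 80% fail under 2:2:1?** Power is 79.97% at 99.0 per TAP arm and 80.01% at 99.1. Starting from 100.8, that is a loss of 1 − 99.1/100.8 = 1.7%, well inside the 5% that the protocol allows for.

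**The case against.** Three points can be made for leaving this alone.

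First, 2:2:1 may be loose shorthand for 2.5:2.5:1, with the table beneath it carrying the real plan. That is plausible, since every other figure agrees with the table. But the document does not say so, and shorthand is unsafe for a figure that has to be entered in a system.

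Second, the effect is very small. A fall of about 1.6 points (80.4% to 78.7% before rounding: 80.36 − 78.74) is not far above the one-point gap between the stated 88% and the recomputed 89.0%, and it is minor beside the uncertainty in an assumed SD of 25. The superiority comparison gains about 3 points. This stands, and it is why the point is minor.

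Third, with all 252 patients randomised at 2:2:1, each arm starts at or above its listed size (about 101, 101 and 50). The TAP arms fall short only through dropout, and the equal split of that loss across arms is an assumption. This also stands. However, the plan itself expects 5% loss, and 80% power is gone at about 1.7%. The document does not show which ratio was entered, so whether any patient is allocated differently from the plan is unknown.

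**Conclusion.** The inconsistency is real: the written ratio is 2:2:1, while the arms, both power statements and the totals all fit 5:5:2. It is minor. With 240 evaluable patients at 2:2:1, non-inferiority power is 78.7% instead of 80.4%, just under the stated 80%, and superiority power is 92.1% instead of 89.0%. With 252 randomised and 5% lost, the corresponding figures are 78.6% against 80.3%, and 92.0% against 88.9%.

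These figures take the protocol's margin, difference, SD and α as given. They treat the primary test as a single one-sided test against the margin of 10, which is the reading that reproduces the stated 80%. The dropout figures also assume equal loss across arms. The trial's ability to answer its question is not in doubt.

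**What to change.** Preferred: in Study Methods II, item d, replace the ratio with 5:5:2 and confirm that the randomisation list was built that way. The 252 patients then split 105:105:42, about 100:100:40 remain after 5% dropout, power is about 80.3% and 88.9%, and no other figure changes.

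Alternative: keep 2:2:1 and restate the arms, in the table and in Data Analysis, as about 96:96:48 evaluable with power of about 79% and 92%. This gives up the 80% target for the primary comparison, and the text should say so. Under either option the totals of 240 and 252 stay. Keeping both 2:2:1 and 100 per TAP arm would instead need 100:100:50, a total of 250, and 250 × 1.05 = 262.5, so 263 recruited by the protocol's own dropout method.

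If randomisation has begun, report the ratio that the list actually uses and align the text with it. The cost is very low: one corrected ratio and a check of the list, or a few restated numbers. The document does not show how the list was built or whether it is already in use.

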### III. During the intraoperative period

- a) Standard anesthesia monitors will be applied: automatic blood pressure cuff, three-lead electrocardiography, capnography, and pulse oximetry will be used continuously.
- b) Induction of general anesthesia will be with propofol 2-3 mg/kg & a non-depolarizing muscle relaxant (choice will be operator dependent). Maintenance of anesthesia will be with an inhalational anesthetic.
- c) The study staff performing randomization will instruct the anesthesiologist or surgeon to either block the transversus abdominis plane with ultrasound, laparoscopy, or no block.
- d) For the block, a standard weight based dose (bupivacaine 0.25% with epinephrine 1:200,000, at a 1ml/kg dose) will be used for both ultrasound-guided or laparoscopic-guided block.
- e) The block is administered between the costal margin and iliac crest in the anterior axillary line at 2 different sites on each side (4 injections total).
- f) For ultrasound-guided TAP block, after the surgeons have completed their portion of the procedure, a member of the anesthesia research team will use sterile technique to prep the abdomen. The block is then placed bilaterally (at 2 different sites on each side of the abdomen) in the anterior axillary line, between the costal margin and iliac crest in the intermuscular plane between the internal oblique and transversus abdominis muscles using ultrasound guidance.
- g) For laparoscopic-guided TAP block, the attending surgeon will perform the block at the conclusion of the procedure under laparoscopic guidance. Bilateral TAP block will be performed in the anterior axillary line between the costal margin and iliac crest. After the needle is passed through the skin, it is continued until 2 distinct “pops” are felt, indicating the needle pierced each of the 2 fascia layers (external oblique and internal oblique fascia).

After injection of the correct plane, a smooth raised area of fluid covered by transversus abdominis muscle is seen with the laparoscope. The laparoscopic vision also assures that the preperitoneal plane is not injected and that the injection does not go intraperitoneal.

- h) Dose of anesthetics, analgesics, local anesthetics, and IV fluid therapy during the operation will be recorded in the anesthesia record as per standard procedure. A copy of the sonographic image will be collected for each patient at the conclusion of the block.
- i) Duration of surgery (from skin incision until closure) and anesthesia (from induction of spinal until discontinuation of the anesthetic drug) will be recorded in the anesthesia record as per standard procedure.

#### IV. PACU

- a) Verbal rating scale (VRS) for pain will be assessed by the PACU RN upon arrival to recovery room, then every 30min interval until discharge.
  - o Requirements for “rescue” analgesic medication will be recorded before discharge.
- b) Any adverse events during the perioperative period will also be noted by PACU RN.

#### V. Following completion of surgery (post-operative):

- a) Anesthesia will be discontinued at skin closure.
- b) Patients will be transferred to the recovery room after emergence from sedation
- c) Treatment of surgical pain prior to discharge from the recovery room: moderate-to-severe pain (VRS > 7): hydromorphone, 1-1.5 mg IV, moderate pain (VRS of 4-6): hydromorphone 0.5 - 1 mg IV., mild pain (VRS 2-3), hydromorphone 0.1-0.2 mg IV. Patient pain control medication will continue with the initial treatment medication for all subsequent rescue doses as needed until recovery room discharge.
- d) Patient nausea, vomiting, or retching will be initially treated with ondansetron 4mg IV. Patients unresponsive to ondansetron will receive metoclopramide 10mg IV.
- e) Patient discharge criteria from PACU will include: awake and alert, and has stable vital signs.

#### VI. Patient evaluation during hospital admission:

- VRS for pain assessment will be utilized to assess pain within the first 72 hours postoperatively and pain scores will be recorded in the patient chart by the nursing staff as per routine CSMC protocol. The average pain scores will be calculated for study analysis.
- VRS scores along with dose for all opioids will be recorded.
- Physical signs and symptoms related to the peripheral nerve block (residual sensory blockade) will be noted.

- Patient satisfaction with the overall technique will also be queried.

Pain evaluation recorded by nursing staff as per standard CSMC guidelines:

- At PACU every 30 minutes
- During admission: 12, 24, 48, and 72 hours postoperatively

Patient satisfaction with analgesia will be assessed at the time of hospital discharge or within 30 days postoperatively by telephone using a patient satisfaction survey:

### **Pain Management Satisfaction Survey**

On a scale of 1-5, how satisfied were you with your postoperative pain management?

Very Unsatisfied	Somewhat Dissatisfied	Neutral	Somewhat Satisfied	Extremely Satisfied
1	2	3	4	5

1 = very unsatisfied.

5 = extremely satisfied.

### **Statistical Considerations**

The following data will be analyzed:

- I. Data to be collected will include the following:
  - a. Demographic details (age, gender, ethnicity, height, weight and BMI)
  - b. Physical factors (height, weight, body mass index)
  - c. American Society of Anesthesiologists Classification
    - i. I – Healthy patient
    - ii. II – Patient with controlled co-existing disease(s)
    - iii. III – Patient with non-controlled co-existing disease(s)
    - iv. IV – Patient with co-morbid condition(s) that are a constant threat to life
    - v. V – Patient not expected to survive surgery

## Data Analysis

### Primary outcome measure:

With a sample size of 100 in each TAP block arm, a two group 0.025 one-sided t-test will have 80% power to reject the null hypothesis that the two groups are not equivalent in morphine (mg) use in the first 24 hours after surgery and rule in favor of the alternative hypothesis that the mean morphine use in the first 24 hours after surgery is equivalent for the two groups or the difference in means ( $\bar{x}_T - \bar{x}_S$ ) is 10 or farther from zero in the same direction, assuming that the expected difference in means is 0 and the common standard deviation is 25.

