### Two group t-test of equivalence in means (equal n's)

	1
Test significance level,	0.025
$\alpha$ (one-sided)	
Equivalence limit difference, <math>\bar{x}_0</math>	10.000
Expected difference, <math>\bar{x}_1</math>	0.000
$\bar{x}_0 - \bar{x}_1$	10.000
Common standard deviation, <math>\sigma</math>	25.000
Effect size, <math>\delta =  \bar{x}_0 - \bar{x}_1  / \sigma</math>	0.400
Power ( % )	80
n per group	100

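### Optional improvement: pre-specify baseline adjustment for 24-hour morphine use, because the plan names only unadjusted t-tests although it already takes plausible covariates

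*Combined protocol and SAP*

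**What the plan says.** The Data Analysis section names two analyses of 24-hour morphine use, both inside power statements. For ultrasound-guided against laparoscopic-guided TAP block, "a two group 0.025 one-sided t-test will have 80% power" with 100 patients per arm, a 10 mg limit, an expected difference of 0 and an SD of 25 mg. The accompanying table is titled "Two group t-test of equivalence in means (equal n's)". For TAP against no TAP, the plan uses "a two group t-test with a 0.05 two-sided significance level" with 100 and 40 patients and a 15 mg difference, "assuming that the common standard deviation is 25 mg". Neither statement mentions a covariate, and no regression model appears elsewhere.

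Study Methods, section II, item b takes a medical history in the preoperative holding area. It includes age and weight, "as well as chronic analgesic usage". Item d then randomises "via online randomization site, sealedenvelope.com, in a 2:2:1 fashion" and gives no stratification factor. The Exclusion Criteria do not name chronic analgesic users, so they can enter any arm.

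**The concern.** Outcome variance that age, weight or chronic analgesic usage explains stays in the residual SD of an unadjusted t-test. It widens the confidence interval that is set against the 10 mg margin. The primary comparison is sized to 80% with almost nothing to spare, so a narrower interval from information already in hand would be useful. Timing matters because an adjusted model is credible as the primary analysis only if its covariates and form are fixed before outcome data are seen. Chosen later, it looks like selection of a favourable result.

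**Working it through.** **Inputs from the Data Analysis section.** TAP versus TAP: n = 100 per arm, SD 25 mg, margin 10 mg, true difference 0, one-sided α 0.025. TAP versus no TAP: n = 100 and 40, difference 15 mg, SD 25 mg, two-sided α 0.05.

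**Assumed input.** R², the share of outcome variance explained by the three covariates within arms. The documents give no value. The range shown is 0 to 0.10.

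**Step 1: the plan's own figure.** SE = 25 × √(2/100) = 3.536 mg. Noncentrality = 10/3.536 = 2.828, df = 198, critical t = 1.972. Noncentral-t power is 80.4%, so the stated 80% at 100 per arm reproduces. The 95% CI half-width is 1.972 × 3.536 = 6.97 mg.

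**Step 2: the adjusted model in the two TAP arms.** Three covariates leave df = 200 − 2 − 3 = 195. Estimating them inflates the variance of the arm difference by an expected factor of 1 + 3/194 = 1.0155. Hence SE = 25 × √(1 − R²) × √(2/100 × 1.0155), and power follows from the noncentral t with noncentrality 10/SE.

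| R² (assumed) | SE, mg | Noncentrality | Net power | 95% CI half-width, mg |
|---|---|---|---|---|
| Unadjusted | 3.536 | 2.828 | 80.4% | 6.97 |
| 0 | 3.563 | 2.807 | 79.8% | 7.03 |
| 0.02 | 3.527 | 2.835 | 80.5% | 6.96 |
| 0.05 | 3.473 | 2.880 | 81.7% | 6.85 |
| 0.10 | 3.380 | 2.959 | 83.7% | 6.67 |

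**Step 3: break-even.** Adjustment pays once 1.0155 × (1 − R²) falls below 1, that is R² above 0.0155/1.0155, or about 0.015. If the covariates explain nothing, the loss is 80.4 − 79.8 = 0.6 points.

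**Step 4: TAP versus no TAP, in its own two-group model.** Unadjusted, SE = 25 × √(1/40 + 1/100) = 4.677 mg, noncentrality = 15/4.677 = 3.207 and df = 138. Power is 89.0%, against 88% stated. With three covariates, df = 135 and the inflation is 1 + 3/134 = 1.0224. Net power is 88.3, 88.9, 89.8 or 91.3% at R² of 0, 0.02, 0.05 or 0.10. The loss at R² of 0 is 0.7 points, and break-even is at R² of about 0.022.

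**The case against.** The strongest reply is that nothing here is broken, and that ANCOVA is a preference whose benefit rests wholly on an assumed R². Much of that stands. No statement in the documents links the three covariates to 24-hour opioid use. The outcome has no baseline value of its own, which is the usual source of a large ANCOVA gain. The history records analgesic rather than opioid use, with no coding, so this covariate may be weak. At R² of 0.02 the gain is in effect nil. What survives is the asymmetry: a fraction of a point at risk, against 1.3 points at R² of 0.05 (81.7 − 80.4) and 3.3 at 0.10 (83.7 − 80.4), with no new measurement.

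Three further points narrow the claim.

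- **The 80.4% has conditions.** It holds for one one-sided test at 100 per arm. The power paragraph and table speak of equivalence, while Background and Significance and the closing sample-size paragraph speak of non-inferiority. Two one-sided 0.025 tests would have about 61% power. A true 2:2:1 split of 240 would put 240 × 2/5 = 96 in each TAP arm and give 78.7% unadjusted.
- **Missing covariates need a rule.** Complete-case fitting would drop patients, and the figures above assume that none are lost.
- **Unequal variances are a separate matter.** Whether the no-TAP arm shares the 25 mg SD, and whether robust standard errors or a three-arm model are needed, is not part of this point.

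A reader might also infer that the covariates could be affected by allocation. The history states that "None of this data will be recorded until written informed consent is obtained", and Subject Recruitment says "After the patient has signed informed consent, they will be randomized to one of three study arms by the study staff". These sentences do not fix whether recording comes before allocation. However, section II lists history, consent and randomisation in that order, and age, weight and past analgesic use cannot be changed by the arm assigned. The practical consequence is minor.

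**Conclusion.** The point holds as an optional, low-cost improvement. The plan leaves baseline information unused in the analysis of its primary outcome, and pre-specified adjustment would probably help a little and could hardly hurt. On the stated SD of 25 mg and 100 per arm, the change in primary power runs from −0.6 points at R² of 0 to +3.3 points at R² of 0.10.

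Two stronger readings are tempting and are not supported. The first is that the unadjusted t-test is wrong or biased, or makes the trial underpowered. Randomisation justifies the unadjusted comparison, and the sample size reproduces under the plan's own assumptions. The second is that adjustment would lift power towards 90%. That needs an R² well above 0.10, for which the documents offer no basis.

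**What to change.** Before any outcome data are seen, state in the Data Analysis section that:

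- the primary analysis is a linear model in the two TAP arms only, with arm, age and weight (both continuous) and chronic analgesic usage (yes/no, with a one-line definition);
- non-inferiority is read by comparing the upper limit of the two-sided 95% CI for laparoscopic minus ultrasound with the unchanged 10 mg margin;
- all randomised patients with an outcome stay in the model, under a simple stated rule for missing covariates, such as mean imputation or a missing indicator;
- each TAP versus no-TAP contrast uses the same covariates in its own two-group model;
- the unadjusted t-tests are kept as sensitivity analyses.

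As minor tidying, add chronic analgesic usage to the data list under Statistical Considerations and say that the covariates are recorded after consent and before allocation.

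The cost is a few sentences of SAP text and three of 198 degrees of freedom. If the covariates prove uninformative, about 0.6 points of power are lost on the primary comparison and 0.7 on TAP versus no TAP. No patient, visit or measurement is added.

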## **STUDY OBJECTIVES**

1. The primary objective of this study is to compare ultrasound-guided block of the transversus abdominis plane (TAP) vs. laparoscopic-guided TAP block, versus no TAP block on opioid consumption in the first 24 hours following colorectal surgery.
2. The secondary objective of this study is to assess the impact of these adjunctive regional techniques on overall patient satisfaction, postoperative pain scores, length of postoperative hospital stay, postoperative ileus, and adverse events directly related or unrelated to TAP block in the 30-day postoperative period.

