## **BACKGROUND AND SIGNIFICANCE**

Postoperative pain can pose significant challenges in the postoperative recovery of patients undergoing major colorectal surgery. Traditionally, opioids have played an important role in treating postoperative pain. It is well established that opioids are highly effective in relieving pain; however opioids are associated with numerous side effects that include nausea, vomiting, constipation, ileus, bladder dysfunction, respiratory depression, pruritus, drowsiness, sedation, and allergic reaction. These opioid side effects, which range in severity, can significantly interfere with discharge home following colorectal surgery. (1) Significant interest exists in the use of local anesthetic based regional anesthesia techniques as a means to extend the analgesic window for patients undergoing colorectal surgery (2). Specifically, the use of the TAP block as an adjunct in postoperative pain control has been widely reported in the anesthesia and colorectal surgery literature (2,3). Historically, the block was performed in a blind fashion with relative success and presently the block is typically performed either with ultrasound guidance or laparoscopic visualization (2,3). While TAP block has shown to be effective in post-operative pain control, the techniques used to place the block have not formally been compared.

We are purposing a prospective, patient-blinded, randomized study of patients undergoing major colorectal surgery to compare TAP block under ultrasound guidance versus laparoscopic visualization versus no TAP block. We hypothesize that laparoscopic-guided TAP block is non-inferior to ultrasound-guided TAP block with respect to perioperative pain control and either technique is superior to no TAP. In addition we will measure procedural time, any adverse events related to the block, overall postoperative analgesic requirement, analgesic duration, postoperative pain scores, length of postoperative hospital stay, incidence of postoperative ileus, and overall patient satisfaction between the three groups.

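### The primary test is worded as equivalence although the trial aims for non-inferiority, and its single one-sided 10 mg limit has no stated direction

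*Combined protocol and SAP*

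**What the plan says.** The combined protocol and SAP describes the main comparison in several places, and they do not agree.

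- **Study Objectives.** The aim is only to compare: "The primary objective of this study is to compare ultrasound-guided block of the transversus abdominis plane (TAP) vs. laparoscopic-guided TAP block". Neither a hypothesis type nor a direction is given.
- **Background and Significance.** The aim is non-inferiority, with a direction: "We hypothesize that laparoscopic-guided TAP block is non-inferior to ultrasound-guided TAP block with respect to perioperative pain control".
- **Data Analysis, Secondary outcome measure.** The closing sample-size paragraph says the total is chosen to show non-inferiority between the two TAP techniques.
- **Data Analysis, Primary outcome measure.** The design is said to have "80% power to reject the null hypothesis that the two groups are not equivalent in morphine (mg) use". The alternative is that mean use "is equivalent for the two groups or the difference in means", written as T minus S, "is 10 or farther from zero in the same direction". The procedure is nevertheless a single test: "a two group 0.025 one-sided t-test will have" that power.
- **Sample-size table that follows.** It is titled as a t-test of equivalence in means and lists one "Equivalence limit difference" of 10, a one-sided alpha of 0.025, an expected difference of 0, SD 25, and 100 per group.

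No second limit, second one-sided test or confidence-interval rule appears anywhere, and T and S are not defined.

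**The concern.** Non-inferiority and equivalence are different claims and need different tests. Non-inferiority rules out one arm being worse by the margin, which one one-sided test does. Equivalence rules out a difference of that size in either direction, which takes two one-sided tests or a confidence interval lying inside two limits. The plan uses the words of the second with the procedure of the first. Followed literally, it would let the trial report that the techniques are equivalent from a test that leaves one side unexamined.

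The missing direction is a separate gap. A one-sided test protects against error in one direction only, so the definition of T minus S decides whether the trial guards against laparoscopic block being 10 mg worse or against ultrasound-guided block being 10 mg worse.

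The alternative also contains differences of 10 mg or more. That may be meant as the untested side of a one-sided alternative. As written, it overlaps the null, because groups that differ by that much are not equivalent.

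**Working it through.** **Inputs** (Primary outcome measure and its table): n = 100 per TAP arm, SD = 25 mg, limit = 10 mg, expected difference = 0, one-sided alpha = 0.025.

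**Step 1: reproduce the stated 80%.**

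- SE = 25 × √(2/100) = 3.536 mg; df = 198; critical t = 1.972.
- Noncentrality = (10 − 0)/3.536 = 2.828.
- Normal approximation: Φ(2.828 − 1.960) = Φ(0.868) = 80.7%.
- Noncentral t: 80.4%.
- Sample size for 80% power: 99 per arm by the normal formula and 100 by noncentral t (79.97% at 99, 80.36% at 100).

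The stated power and n are therefore correct for one one-sided non-inferiority test.

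**Step 2: effect of the undefined direction.** The test passes when T minus S is shown to be below 10 mg. For a true value d of T minus S, the noncentrality is (10 − d)/3.536.

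| True T − S (mg) | Noncentrality | Probability of passing |
|---|---|---|
| +10 | 0 | 2.5% |
| +5 | 1.414 | 29.0% |
| 0 | 2.828 | 80.4% |
| −5 | 4.243 | 98.8% |
| −10 | 5.657 | 99.99% |

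If T is laparoscopic, a laparoscopic excess of 10 or 5 mg is d = +10 or +5. If T is ultrasound, the same excess is d = −10 or −5. Hence:

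| True laparoscopic excess | Passes if T − S = laparoscopic − ultrasound | Passes if T − S = ultrasound − laparoscopic |
|---|---|---|
| 10 mg | 2.5% | 99.99% |
| 5 mg | 29.0% | 98.8% |

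**Step 3: why passing does not show equivalence.** With T as laparoscopic, the test passes 99.99% of the time when laparoscopic block truly needs 10 mg less. That is proper behaviour for a non-inferiority test, but arms 10 mg apart are not equivalent by the plan's own limit.

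**Step 4: power if equivalence were meant.** The documents give one limit; assume −10 and +10 mg. At a true difference of 0, each one-sided 0.025 test fails with probability 1 − 0.8036 = 0.1964, and both failing together is negligible. Power is therefore about 1 − 2 × 0.1964 = 60.7%. Exact integration over the distribution of the sample SD gives:

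| Alpha per side | Power at 100 per arm | n per arm for 80% |
|---|---|---|
| 0.025 | 60.7% | 133 |
| 0.05 | 76.0% | 108 |

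The stated 80% at 100 per arm thus fits non-inferiority, and does not fit equivalence within these assumed limits.

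**The case against.** The strongest defence is that the intended design can be recovered. The Background names the hypothesis and its direction, the sample-size summary repeats non-inferiority, and the single one-sided test with one limit has the form of a non-inferiority test. The 80% reproduces on that reading and not on the two-sided one. Benefits to Study Subjects treats lower opioid intake as the gain, so the harmful direction can be inferred. The clause about differences of 10 mg or more may be a clumsy way of saying equivalent or better. On this view no design figure moves, and the reversed-direction and two-sided figures describe readings that the Background argues against.

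Much of this stands. No arithmetic is wrong, non-inferiority is the best-supported reading, the reversed-direction pass rates are hypothetical, and the equivalence powers rest on a lower limit the documents do not give. The objective's neutral wording contradicts nothing; it merely fails to settle the question. Some symbols may also have suffered in reading the PDF, though that does not explain why T and S are never defined.

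The defence does not remove the fault. The section that defines the primary test states a different hypothesis from the Background, and the reader has to infer both the claim and the direction. Labels elsewhere do not help: the randomization list calls ultrasound Group 1 and laparoscopic Group 2, while the secondary-outcome paragraph uses Group 1 for No TAP and Group 2 for TAP. Left like this, the choice between equivalent and non-inferior could be made after the data are seen.

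**Conclusion.** The concern holds. The primary hypothesis is stated inconsistently, and the passage that defines the test would permit a conclusion the test cannot support. The fault lies in the hypothesis and decision rule, not in the calculation: 100 per arm gives 80.4% power for one-sided non-inferiority, given SD 25 mg, a 10 mg margin and no true difference. On the same inputs, a true laparoscopic excess of 10 mg passes 2.5% or 99.99% of the time depending solely on how T and S are assigned. If the word equivalent were meant, and limits of −10 and +10 mg are assumed, power would be 60.7% or 76.0% depending on the alpha per side, below the stated 80%. Because this governs what the primary analysis may claim, it must be corrected before the data are analysed.

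**What to change.** In Primary outcome measure, replace the hypothesis wording with:

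- H0: mean(laparoscopic) − mean(ultrasound) ≥ +10 mg, for 24-hour postoperative use in morphine equivalents.
- H1: mean(laparoscopic) − mean(ultrasound) < +10 mg.
- One-sided t-test at 0.025. Non-inferiority is declared if the upper limit of the two-sided 95% confidence interval for laparoscopic minus ultrasound is below +10 mg.
- With 100 per arm, SD 25 mg and a true difference of 0, power is 80%.

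Delete the equivalent and not-equivalent wording and the clause about differences of 10 mg or more. Retitle the table as a non-inferiority t-test and show its limit as the non-inferiority margin, laparoscopic minus ultrasound, +10 mg.

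This costs only a change of wording: sample size, margin and alpha stay as they are, and no extra patients are needed.

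If the sponsor does intend equivalence, the plan must state both limits and the alpha per side, and restate the power at 100 per arm. With limits of −10 and +10 mg that is about 61% at 0.025 per side or 76% at 0.05 per side; reaching 80% would take 133 or 108 per arm.
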